# 7.2 **Baseline Testing/Prestudy Evaluation**

Participants will undergo a Screening Evaluation to be assessed for study eligibility. The informed consent form, medical records release and tissue release form will be signed. Participants must have biopsy confirmed high grade cervical squamous intraepithelial lesions (i.e., CIN3 lesions and CIN2 lesions diagnosis confirmed by positive p16 immunohistochemistry staining) within 12 weeks prior to the Baseline Visit.

Participants will be evaluated for concomitant medications, medical history and baseline symptoms and signs.

Participants will undergo a brief physical exam including weight, height, vital signs including temperature, blood pressure, and heart rate. Performance status will be collected.

Blood will be collected for complete blood count with differential (CBC-diff) and comprehensive metabolic panel (CMP) and HIV test. Urine will be collected for urinalysis, tests on pregnancy, Chlamydia, and Gonorrhea.

A symptom diary for recording adverse events will be provided to participants at this visit.

#### 7.3 Evaluation During Study Intervention

Participants who meet the eligibility assessment will return to the clinic for a Baseline Visit. Vital signs will be collected including weight, temperature, blood pressure and heart rate. Participants will complete tobacco and alcohol assessment forms. Urine will be collected for pregnancy test. Adverse events and concomitant medications will be reviewed.

Participants will undergo colposcopic examination with digital imaging of the cervix and cervical specimen collection (cericovaginal lavage, swab of the cervix, swab of the vagina, and cervical brushing for research endpoints and banking; see section 10.2.2 for detailed information). Blood and urine will be collected and banked for future research. Participants will receive education regarding 5-FU self-application, condoms and contraception use, and scheduling information about study visits for imiquimod application. They will receive an initial supply of the following: intravaginal 5-FU, condoms, pregnancy test kits and instructions on agent applications. Participants will be supplied to participants in a commercially available tube with vaginal applicators for 4 applications. Participants will be shown how to remove the 5-FU cream from the tube to fill the applicator with 2 grams of the cream prior to each self-application. If needed, participants may use lidocaine jelly or a topical protective barrier cream to the vulva and/or take oral ibuprofen to minimize vulvar irritation or pain from the application of study agent. If the participant experiences an allergic reaction (swelling, rash, hives), she may use diphenhydramine and should notify the study physician. Use of these products will be recorded on the study calendar.

Participants will self-apply 5-FU intravaginally on weeks 1, 3, 5 and 7. They will be contacted via phone call, text or email to remind them to use the 5-FU, to answer questions participants may have and to review AEs and concomitant medications. Participants will also be reminded to perform pregnancy testing prior to each time they use the study medication, to avoid sexual activity for at least 48 hours after each application of study medication, and to use two forms of birth control including condoms and one other form of contraception when participating in sexual activity. Agent application will be delayed until the end of menstrual cycle if application date occurs during menses. No dose will be applied any sooner than 7 days apart even in the setting of dose delay. Participants will record study agent applications on study calendar. If a safety concern is identified during the regular contact, participants will be asked to come in for an interim clinic exam.

Participants will return to the clinic every other week (weeks 2, 4, 6 and 8) to assess safety and compliance and for provider applications of imiquimod. Prior to study visits, participants will be reminded to bring unused applicators, tube of 5-FU, symptom diary and study calendar to the study visits. Visits may be delayed due to menstrual cycle. No dose will be applied any sooner than 7 days apart even in the setting of dose delay. At each of these interim visits, participants will be assessed for weight, vital signs, concomitant medications, review of symptom diary and study calendar with study staff, and undergo a urine pregnancy test. The tube of 5-FU cream will be weighed at each visit to check compliance. Participants will undergo a colposcopic examination with digital imaging of the cervix and examination of genital tissues

for any adverse outcomes. They will undergo a urine pregnancy test prior to receiving application of study agent. Imiquimod will be applied by the provider directly onto the cervix. If there is any evidence of disease progression, they will undergo biopsy confirmation. Participants will be taken off study for biopsy confirmed invasive squamous cervical cancer or cervical adenocarcinoma or adenocarcinoma-in-situ. Similarly, participants will be reminded to avoid sexual activity for at least 48 hours after each application of study medication, and to use two forms of birth control including condoms and one other form of contraception when participating in sexual activity.

At the Week 8 Visit, participants will also undergo blood collection for CBC with diff and CMP. Participants will return unused agents. At this point, they will be offered the option to continue with study participation for applications of 5-FU and imiquimod on alternating weeks for an additional 8 applications (extension phase). Participants who opt into the extension phase will be provided with 5-FU for 4 additional applications. The timeline and visits for the extension phase will be the same as for the 8 applications of the initiation phase, however, cervical and vaginal specimens, blood, and urine collection for research endpoints and for future research will only be collected at this visit for participants who choose to continue participation for an additional 8 weeks.

# 7.4 Evaluation at Completion of Study Intervention

The use of the study agents will be completed after 8 applications of agents or after 16 applications if the participant opts to continue participation for an additional 8 applications of treatment.

Four to six weeks after 8 (or 16) applications of agent (or 4-6 weeks after the last agent application, if off agent before completing the 8 or 16 application cycle), participants will return for an End of Study Visit. Participants will be assessed for weight, vital signs, and concomitant medications; review symptom diary and study calendar with study staff. Participants will complete tobacco and alcohol assessment forms and will be given the option to complete a survey about their experiences while participating in the study. Participants who completed participation in the study and were not given the opportunity to complete the survey at that time may do so by telephone, mail or email once verbal consent has been obtained. They will undergo blood and urine collection for future research. In addition, a blood sample will be collected for CBC with diff and CMP and urine will be collected for a urinalysis and urine pregnancy test. Participants will undergo a colposcopic examination with digital imaging of the cervix. Cervical and vaginal specimens will be collected for research endpoints and future research. Additional cervical cells will be collected and sent to the institutional pathology lab for Pap smear and HR-HPV testing. Participants will be scheduled for LEEP or Cold Knife Cone procedure at this time. If participants decline LEEP or are young women with CIN 2 whose standard of care recommendation had been to observe disease for 6 months, then participants will be given the option to first undergo colposcopy-directed biopsy to assess for residual disease. If subjects opt to have colposcopy-directed biopsy first, then subjects will undergo a minimum of 2 cervical biopsies (one will be at the site of previously noted disease, second will be an endocervical curettage) for histopathological confirmation to verify no microscopic disease. If there is histologic confirmation of residual high-grade squamous intraepithelial lesions or ASCH/HSIL pap, participants will undergo a LEEP or cone biopsy at future clinical visit according to current clinical care recommendations. If they have evidence of regression (LSIL or normal histology or LSIL, ASCUC, normal pap), participants will be recommended to return 6 months later to repeat colposcopic examination with Pap smear and HR-HPV (to be performed as the standard of care).

Digital photos will be evaluated for repeat assessment and lesion measurement by a board-certified Gynecologist or Gynecologic Oncologist.

# 7.5 Post-intervention Follow-up Period

Study staff will contact the participant within 2 weeks of receiving pathology reports of the colposcopically-directed biopsies. Women with CIN 1-3 disease will be offered current clinical management. Any participant with more severe lesions, such as adenocarcinoma-in-situ or cancer, will be referred for management by gynecologic oncology.

The study team will collect results from the follow-up cervical exams/procedures/tests performed within 14 months after the End of Study Visit from the medical records for all participants.

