#### Clinic visits for imiquimod application

(Initiation phase: weeks 2, 4, 6, 8; Optional extension phase: weeks 10, 12, 14, 16\*\*)

Colposcopy with digital imaging of the cervix (and further management if evidence of disease progression)

Application of imiquimod by provider, collect unused agents

Weight, vital signs, urine pregnancy test, concomitant medications, AE evaluation

Additional procedures at week 8 visit only if continuing into optional extension phase\*\*:

Blood for clinical labs, cervical specimen, blood, and urine collection for research endpoints

¥

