#### 2. BACKGROUND

#### 2.1 Cervical Cancer

**High-risk human papillomavirus (HR-HPV) infection is a precursor to cervical cancer, the leading cause of gynecologic cancer worldwide.** HR-HPV genotypes 16 and 18 are associated with approximately 70% of cervical cancers. Roughly 25 million women in the U.S. are actively infected with HPV, and an estimated 80% of sexually active women will contract genital HPV by age 50. While most HR-HPV infections are transient, persistent HR-HPV infections are considered the most significant risk factor for the development of high-grade cervical intraepithelial lesions (CIN 2-3) and cancer. Long standing clinical practice has been to treat all high grade CIN similarly by recommending immediate treatment for all women regardless of age or risk factors. Current clinical guidelines recognize that the prevalence of HPV is high in young women (particularly in the 3rd decade of life) and that disease can be transient.  Therefore, intervals of follow up have been lengthened and options for observation of high grade CIN 2 lesions have been encouraged.  This approach has been implemented to decrease the over-treatment of women of childbearing age, which can put them at a higher risk for preterm delivery, pain, and bleeding.

**Current screening for and management of cervical precancer is based on surveillance and destructive surgical therapy.** Pap smear surveillance has significantly reduced the incidence of and mortality from cervical cancer by early identification of high-grade cervical intraepithelial lesions and preventative treatment through excisional or ablative surgical procedures. A large majority of women with low-grade CIN (also known as CIN 1) regress to normal within 12-36 months (Figure 1). Approximately 40-58% of CIN 2 lesions regress spontaneously, 30-35% persist, and 10-22% progress to CIN 3. More than 12% of women with CIN 3 will advance to invasive cancer over 5-10 years. A key variable in risk is age; young women are more likely to experience regression of cervical dysplasia. Therefore, current clinical guidelines suggest observation with Pap smears and colposcopies at 6 month intervals for "young women" with high-grade CIN. The term "young woman" is loosely defined as women planning future pregnancies.

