# 4. PARTICIPANT SELECTION

# 4.1 Inclusion Criteria

- 4.1.1 Women with biopsy confirmed high grade cervical squamous intraepithelial lesions (i.e., CIN3 lesions, and CIN2 lesions with diagnosis confirmed by positive p16 immunohistochemistry staining) within 12 weeks of Baseline Visit
- 4.1.2 Age 18-45 years
- 4.1.3 Karnofsky ≥70%

4.1.4 Participants must have normal organ and marrow function as defined below:

Leukocytes	$\geq$ 3,000/microliter
Absolute neutrophil count	$\geq$ 1,500/microliter
Platelets	$\geq$ 100,000/microliter
Serum creatinine	$\leq$ the upper institutional limits

4.1.5 Participants must have a negative HIV antibody/antigen test and negative C. trachomatis/N. gonorrhea NAAT.

UAZ2016-08-02

4.1.7 Ability to understand and the willingness to sign a written informed consent document.

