# 13.5 Secondary Objectives, Endpoints, Analysis Plans

The secondary objectives include describing the response (composite endpoint based on histologic regression and clearance of HR-HPV) to intravaginal 5-FU and imiquimod and type specific HR-HPV clearance and measuring changes in the expression of biomarkers of local immune activation (including IFN- $\alpha$ 2, IFN-Y, IL-10, IL-12, IL-1 $\alpha$ , -1 $\beta$ , -6, -8, MIP-1 $\alpha$ , TNF) after treatment with self-administered intravaginal use of 5-FU and imiquimod. The response and type-specific HR-HPV clearance will be reported along with their 95% confidence intervals. For each biomarker, the mean change and the associated standard deviation will be reported. Analyses will be performed on all participants who provide post-intervention specimens for endpoint evaluation. Assume an attrition rate of 15% (for completing intervention and providing post-intervention specimens). There will be at least10 participants available for the secondary analyses. Based on a sample size of 10, it allows us to construct a 95% confidence interval for the overall response and clearance rate, respectively, with a width  $\leq 0.72$ . It also allows us to construct a 95% confidence interval for the overall change in expression of each biomarker with a distance from the mean change  $\leq 0.72$  standard deviations. With an anticipated attrition rate of 15%, we will try to reduce the fraction of participants with missing outcomes as much as possible. Also, multiple imputation techniques will be used to handle missing data. Similar to the primary endpoints, each of the secondary endpoints will be also reported by whether or not the participants continue to the expansion phase.

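### Progression is looked for on study and follow-up results are collected for 14 months, but no endpoint or planned analysis names progression or uses those results

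*Combined protocol and SAP*

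**What the plan says.** **Looking for progression.** Colposcopy is scheduled at each imiquimod clinic visit and at End of Study (7.1). During treatment, 7.3 says: "If there is any evidence of disease progression, they will undergo biopsy confirmation". It continues: "Participants will be taken off study for biopsy confirmed invasive squamous cervical cancer or cervical adenocarcinoma or adenocarcinoma-in-situ". Exit histology comes from LEEP, cone or colposcopy-directed biopsy (7.4). After that, 7.5 provides: "The study team will collect results from the follow-up cervical exams/procedures/tests performed within 14 months after the End of Study Visit". The source is the medical records of all participants.

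**Why progression is relevant.** Section 2.1 states: "Approximately 40-58% of CIN 2 lesions regress spontaneously, 30-35% persist, and 10-22% progress to CIN 3". It also puts advance from CIN3 to invasive cancer at more than 12% over 5-10 years. Section 2.2 says women with CIN3 have no alternative to surgery.

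**What is analysed.** Safety in 8.1 and 13.4 is the number of women with a dose-limiting toxicity (DLT), which must be at least possibly related. Tolerability is the number unable to apply half the treatment because of DLT. The secondary endpoints (8.2) are histologic regression combined with high-risk HPV clearance, genotype-specific clearance and immune biomarkers, all from baseline to study exit. Section 13.5 says: "The response and type-specific HR-HPV clearance will be reported along with their 95% confidence intervals". It analyses women with post-intervention specimens and applies multiple imputation to missing data. Section 13.7 summarises all adverse events.

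**The concern.** The trial is to decide whether the regimen goes forward, and the only stated no-go rule is DLT in 33% or more (13.4). Women receive the regimen while excision waits, so worsening of the lesion is one of the outcomes the next trial's designers will ask about. Section 13.1 says extension-phase data will further assess safety, but no planned result describes what happens to the disease over the longer wait. Followed as written, the report could call the regimen feasible without stating how many women had a worse diagnosis at exit or in the next 14 months, although the data would be in hand.

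**Working it through.** **1. The plan's own figures.** No figure for progression is given. The DLT table reproduces with X ~ Binomial(12, p) and P(X ≥ 4): 2.6%, 20.5% and 50.7% at p = 10%, 20% and 30%. It is correct, and progression does not enter it.

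**2. Data against analysis.**

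| Source | Analysis that names it |
|---|---|
| Biopsy for suspected progression at imiquimod visits (7.3) | None by name; possible through 13.7 |
| Exit histology (7.4) | 13.5, as response or not |
| Records for 14 months after End of Study (7.5) | None |

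**3. The adverse-event route.** Section 11 defines adverse events to include disease arising during participation, related or not. The Appendix B table takes precedence for genital events (11.1.3.1) and has a biopsy row: intraepithelial neoplasia 1, neoplasia 2, carcinoma in situ and invasive carcinoma as Grades 1 to 4. Progression entered as an adverse event would therefore reach 13.7. If judged at least possibly related, Grade 2 or more and lasting over 5 days, it would also meet the DLT wording. But no section says exit or follow-up histology is entered as an adverse event. The row does not name grade 3 neoplasia. Every participant already has CIN2 or CIN3 at entry, and no rule defines worsening. Section 11.1.1 gives recording a start but no end.

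**4. How cases enter 13.5.** CIN2 at entry with CIN3 at exit is not regression, so it falls with persistent CIN2. A woman taken off study for cancer or adenocarcinoma-in-situ may have no post-intervention specimen. She is then outside the set, or her outcome is imputed and could be drawn as a response. Dropping one known non-responder from 12 multiplies the response proportion by 12/11 = 1.09.

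**5. Outer limit of the wait.** Inputs are the qualifying biopsy ("within 12 weeks of Baseline Visit"), End of Study ("Four to six weeks after 8 (or 16) applications of agent"), 5 business days of visit slack and 2 weeks to the procedure (notes to 7.1). Week 1 is assumed to start at Baseline.
- With the extension: 12 + 15 + 6 + 1 + 2 = 36 weeks.
- Without it: 12 + 7 + 6 + 1 + 2 = 28 weeks.

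Menstrual delays would add to both.

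**6. Illustrative numbers.** Assume 4 to 8 of 12 women enter with CIN2, and that the 10-22% applies over the study.
- Expected progressions: 4 × 0.10 = 0.4 to 8 × 0.22 = 1.76.
- P(at least one): 1 − 0.90⁴ = 34% to 1 − 0.78⁸ = 86%.

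**7. Precision of a reported count (Clopper-Pearson 95%).**
- 0/12: upper limit 1 − 0.025^(1/12) = 26.5%.
- 1/12: 0.2-38.5%.
- 2/12: 2.1-48.4%.
- Zero events in an entry-grade subgroup of 6: upper limit 1 − 0.025^(1/6) = 45.9%.

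**8. Text on adenocarcinoma-in-situ.** Section 3 omits it from the findings that take a woman off study during treatment; 7.3 includes it. For results after End of Study, Section 3 groups it with CIN 1-3, while 7.5 groups it with cancer for referral.

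**The case against.** A reader might infer that progression cannot be reported anywhere. The documents do not support that. Section 13.7 covers all adverse events, the definition is broad, and an on-study invasive cancer would be an adverse event. The gap is that the route is unspecified.

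A reader might infer that events in the 14-month records fall outside adverse-event recording. That is not established either. No end date is given, the 30-day minimum in 11.2.3 concerns only follow-up of serious events that are unrelated or unlikely to be related, and 8.4 ends participation when required follow-up is complete. The text is silent.

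Nor can it be said that all progressors are pooled as non-responders; step 4 shows the gravest cases may be treated otherwise. Against that, a note to 7.1 asks women who terminate early to return for End of Study procedures, and 13.6 reports on the intent-to-treat population. Some off-study women may therefore supply an outcome, but no rule says how it counts.

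Other points stand in part. An apparent CIN2-to-CIN3 change may reflect undersampling: entry is by biopsy, while exit may be a LEEP or cone, which Section 2.1 describes as removing 1-3 cm. There is no control arm, so a count cannot be attributed to the wait. Observation is already an option for some young women with CIN2 (2.1, 7.4), so not all the waiting is caused by the trial. CIN2 and CIN3 are deliberately one high-grade entry category, and splitting them leaves small cells. These limit interpretation; they do not justify leaving the count out.

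**Conclusion.** The point holds as a reporting and analysis gap. No endpoint or planned analysis names progression, the response endpoint does not separate it from persistence, women taken off study for cancer or adenocarcinoma-in-situ have no stated outcome, and the 14-month results have no analysis. This rests on the text alone.

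The size is uncertain. The 36-week figure is an outer limit that assumes the optional extension and includes up to 12 weeks before Baseline. The 34-86% rests on an assumed case mix and on a spontaneous rate for CIN2 generally, quoted without a time frame and applied here to treated, p16-positive women. Neither figure shows that the regimen or the wait causes progression. The sample size, DLT rule and tolerability tables are unaffected.

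**What to change.** 1. In 13.5, tabulate exit histology among all treated women as regressed, persistent or progressed (CIN2 to CIN3, or any adenocarcinoma-in-situ or invasive cancer), by entry grade and by exit method (LEEP/cone or directed biopsy), with exact 95% intervals. Show women without exit histology separately so that the rows add up.
2. In 13.5, count women with biopsy-confirmed progression, including those taken off study, as non-responders and do not impute them.
3. In 13.7, state whether histologic progression is recorded as an adverse event. List each case with entry grade, applications received and weeks from qualifying biopsy to diagnosis.
4. Summarise the 14-month results descriptively, beside the number of women with any record.
5. Reconcile Section 3 with 7.3 and 7.5 on adenocarcinoma-in-situ.

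The cost is wording, one table and a case listing from data already collected, with no new visit or procedure. The report should state the limits: small descriptive counts, no control arm, possible undersampling at entry, and follow-up that depends on who returns.

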# 7.6 Methods for Clinical Procedures

Colposcopy and biopsy will be carried out according to standard clinical procedures. Colposcopic images will be obtained at low magnification (10X/20X) with acetic acid according to standard clinical practice. Cervical biopsies will be taken after application of acetic acid.

